23.0	Resources Available.....	18
24.0	References.....	19

PROTOCOL TITLE: Prospective Randomized controlled trial comparing liposomal bupivacaine to bupivacaine Interscalene blocks for total shoulder arthroplasty surgery

VERSION DATE: 7/6/2020

ABBREVIATIONS/DEFINITIONS

- LB/ liposomal bupivacaine
- TSA/total shoulder arthroplasty
- QOR/Quality of Recovery
- RCR/rotator cuff repair
-

PROTOCOL TITLE: Prospective Randomized controlled trial comparing liposomal bupivacaine to bupivacaine Interscalene blocks for total shoulder arthroplasty surgery

VERSION DATE: 7/6/2020

STUDY SUMMARY

Study Title	Prospective Evaluation of Liposomal bupivacaine in Total Shoulder Surgery
Study Design	Prospective randomized double blind
Primary Objective	Total opioids in 72 hours
Secondary Objective(s)	Pain scores within 72 hours, QOR at 72 hours and 14 days, Number of phone calls to surgeon, adverse events, time to discharge
Research Intervention(s)/Investigational Agents	Liposomal bupivacaine and bupivacaine vs bupivacaine
Scientific Assessment	HRPP facilitated scientific assessment
IND/IDE # (if applicable)	Study Medication has been approved for use in shoulder surgery April 6, 2018
IND/IDE Holder	Pacira Pharmaceuticals
Investigational Drug Services # (if applicable)	N/A
Study Population	Adult patients aged 18 and older who are undergoing total shoulder arthroplasty
Local Sample Size (number of participants recruited locally)	90

PROTOCOL TITLE: Prospective Randomized controlled trial comparing liposomal bupivacaine to bupivacaine Interscalene blocks for total shoulder arthroplasty surgery

VERSION DATE: 7/6/2020

1.0 Objectives

Purpose: To determine if LB plus bupivacaine provides superior pain control compared to bupivacaine alone when injected in an interscalene block for patients undergoing total shoulder arthroplasty surgery.

2.0 Background

Significance of Research Question/Purpose: Liposomal Bupivacaine (LB) has not been adequately studied in peripheral nerve blocks and has yet to be studied for use in interscalene blocks for Total Shoulder Arthroplasty (TSA) patients. It has been studied in Rotator Cuff Repairs (RCR) surgery and showed superior analgesia compared to bupivacaine.

Preliminary Data: It is our standard of care to use this medication in an interscalene block at the U of MN for patients undergoing TSA. A retrospective study performed showed superior analgesia and less opioids in those having LB plus bupivacaine vs bupivacaine or ropivacaine only blocks.

Existing Literature: Vandepitte et al showed that LB plus bupivacaine was superior to bupivacaine when used in interscalene nerve block for patients undergoing major shoulder surgery (both RCR and TSA).

3.0 Study Endpoints/Events/Outcomes

Primary Endpoint/Event/Outcome: To determine if LB plus bupivacaine in an interscalene block results in less opioid use over 72 hours compared to bupivacaine only for TSA surgery.

Secondary Endpoint(s)/Event(s)/Outcome(s):

- To determine if LB plus bupivacaine in an interscalene block results in less pain over 72 hours as compared to bupivacaine only in an interscalene block for TSA surgery. Assessed via total pain scores (Use of Visual Analog Scale)
- To determine if LB plus bupivacaine in an interscalene block results in improved (Quality of Recovery) QOR at 72 hours and 14 days as compared to bupivacaine only in an interscalene block for TSA surgery. Assessed via QOR 15 patient survey.
- To determine if LB plus bupivacaine in an interscalene block results in fewer phone calls to the surgeon within 72 hours as compared to bupivacaine only in an interscalene block for TSA surgery.

PROTOCOL TITLE: Prospective Randomized controlled trial comparing liposomal bupivacaine to bupivacaine Interscalene blocks for total shoulder arthroplasty surgery

VERSION DATE: 7/6/2020

- To determine if LB plus bupivacaine in an interscalene block hastens readiness for hospital discharge compared to bupivacaine only in an interscalene block for TSA surgery.

4.0 Study Interventions/Investigational Agent(s)

Description: LB is a long acting local anesthetic. It is liposome encapsulated bupivacaine which allows for prolonged release of bupivacaine over a 72-hour period. Bupivacaine is a medium acting local anesthetic which provides between 6 and 24 hours of analgesia when used in a peripheral nerve block. Both medications are standard of care for use in interscalene blocks here at the U of MN. Acetaminophen is a medication used to treat pain, gabapentin is a gabapentinoid which is used to treat postoperative pain, and Celebrex is a selective COX-2 inhibitor also used to treat pain.

Drug/Device Handling: The LB will be stored in a locked pyxis fridge in a box labeled Liposomal Bupivacaine. The anesthesiologists in charge of regional anesthesia the day the procedure will be informed will write the order for dispensing the medication and the block per standard of care. It will be retrieved by the PI and sub I's for use in the interscalene blocks.

Biosafety: Per standard of care

Stem Cells: N/A

5.0 Procedures Involved

Study Design: Level I randomized prospective outcomes study comparing two groups of patients. Patients will be assigned either to Liposomal Bupivacaine plus bupivacaine for an interscalene block or they will receive bupivacaine for an interscalene block injection.

Study Procedures: After consenting to the study (either in clinic or the PAC clinic) and completion of the preoperative process (per standard of care), a randomization scheme from a random number generator will be followed to ensure equal likelihood of group assignment. The patient will be placed in the supine position with the head of the bed elevated 30 degrees with standard ASA monitors applied. Sedation will be provided with midazolam 0-2mg and propofol 0-50 mg. The interscalene groove will be identified with the ultrasound. Using sterile technique, a 21g Nerve block needle will then be inserted and advanced under ultrasound guidance until it is in the interscalene groove. Once in the interscalene groove, 20 mL of local anesthetic will be injected, with 10mL deposited at the top of the brachial plexus and 10mL at the bottom. In the study group, 5 mL of each 0.5% bupivacaine and LB will be injected at each location.

PROTOCOL TITLE: Prospective Randomized controlled trial comparing liposomal bupivacaine to bupivacaine Interscalene blocks for total shoulder arthroplasty surgery

VERSION DATE: 7/6/2020

The control group will have 20mL of 0.5% bupivacaine divided between the injection sites. Patients would be required to take a dose of acetaminophen 975 mg oral, gabapentin 300 mg oral, and Celebrex 400 mg oral prior to surgery (per standard of care). The patient will be monitored (vital signs, respiratory status and oxygen saturation) in the preoperative area until he/she is brought into the operating room for their procedure. A working block prior to surgery will be confirmed via sensory testing of the shoulder.

All patients will undergo a standard induction with propofol 1.5-3.0 mg/kg, lidocaine 60-100 mg, ondansetron 4 mg, dexamethasone 10 mg and ketamine 0.25 mg/kg. An LMA or ETT will be placed and an opioid sparing technique will occur. Standardized maintenance will be a propofol infusion without neuromuscular blockers. 25-50 mcg of IV Fentanyl will be utilized for increases in heart rate greater than 20% or increases in systolic blood pressure above baseline.

Once in the operating room the surgeon will use 10 mL of 0.25% bupivacaine for skin, subcutaneous, and intraarticular injection.

When the operation is complete, the patient will be brought to the post-operative care unit (PACU). The patient will receive IV fentanyl for a pain score of greater than 5 on the visual analog scale. If more than 200 mcg of fentanyl is given and pain still remains above a 5 then IV hydromorphone will be used. A dose of 5-10 mg of oral oxycodone (or 2-4 mg of oral hydromorphone) will be given as soon as the patient is able to tolerate oral medication per standard protocol: If their pain score is 4-6 (on the Visual Analog Scale) then 5mg oral oxycodone (2 mg hydromorphone) can be administered, if their pain is between 7 to 10 then 10 mg of oxycodone (or 4 mg of hydromorphone) can be administered. The patient will either be discharged to a hotel or brought to the ward where each day a member of the research team will evaluate (if in the hospital) or call (if discharged to hotel) the patient for signs of complications and ask the patient their maximum pain score, total opioids and non-opioid pain medication used, and length of stay. If patients have met criteria for discharge to home including pain <4/10, independence of intravenous analgesia, and medical stability for discharge but are awaiting placement, the time of discharge for the purposes of the study will be the day they have met such criteria as opposed to the actual time of discharge as this can vary depending on patient placement.

Once the patient meets discharge criteria, they will be discharged home where each day they will fill out a pain diary. Additionally, a member of the research team will call the patient for signs of complications and ask the patient their current pain score, total opioid pills taken and non-opioid pain medication taken

PROTOCOL TITLE: Prospective Randomized controlled trial comparing liposomal bupivacaine to bupivacaine Interscalene blocks for total shoulder arthroplasty surgery

VERSION DATE: 7/6/2020

at 24, 48, and 72 hours postoperatively. Additionally, they will perform a Quality of Recovery Score survey at 72 hours, and 14 days postoperatively.

While in the hospital all patients will receive a standardized multimodal pain medication regimen. Acetaminophen 975 mg q6 hours, ibuprofen 600mg q6 hours and prn oxycodone 5-10 mg q4 hours or 2-4 mg hydromorphone oral every 4 hours. All patients will be discharged with 30-40 pills of 5 mg oxycodone or 30-40 pills of hydromorphone 2 mg with instructions to take 5-10 mg oxycodone for severe pain every 4 hours as needed or 2-4 mg every 4 hours hydromorphone as needed for severe pain. Patients will be instructed to start with the lower dose, but can repeat the dose if needed up to 10mg oxycodone or 4mg hydromorphone every 4 hours if needed.

Assessments: Post-operatively patients will be evaluated at 2 and 6 hours post-operatively by a blinded research staff. This person will not be aware of the patient's mode of analgesia. The patients will be contacted via in person assessment or via telephone at 24, 48, and 72 hours +/- 5 hours. Patients will be asked to rate their pain on scale of 0-10. The amount of opioids used by the patient will be recorded by study personnel as will any other adjuvant pain medication used. The time in phase 1 and phase 2 of PACU will be recorded. The patients will be asked at 72 hours post-injection if they would undergo an interscalene block with their medication again or if they would choose a different form of pain management (ex: higher doses of pain medications). Patients will fill out a Quality of Recovery Survey at 72 hours and 14 days, and be assessed for block related complications at this time. As part of the research, patients also will undergo diagnostic ultrasound of their diaphragm on POD 1. All complications will be recorded including:

- Failure of the block
- Wound infections
- Subsequent procedures
- Complications related to placement of the interscalene block including nerve injury, prolonged sensory loss greater than three days, prolonged arm weakness greater than three days
- Opioid related side effects of nausea and/or vomiting
- Local anesthetic toxicity as evidenced by seizures or cardiovascular collapse without other reasonable etiology

All data will be recorded on the Clinical Diagnostic Sheet and will then be given to the research coordinator for manual data entry. Data collection will continue until POD #14. At that time study participation will be terminated. Should patients be re-admitted to the hospital in the next two weeks (Up to POD 30) for pain, a notation will be made in study records.

An analysis of the total cost of analgesics will be tabulated at the conclusion of the study to determine the most cost effective treatment option as this will be

PROTOCOL TITLE: Prospective Randomized controlled trial comparing liposomal bupivacaine to bupivacaine Interscalene blocks for total shoulder arthroplasty surgery

VERSION DATE: 7/6/2020

added into the cost of hospitalization including the number of days each patient spent in the hospital.

Blinding Procedure: A random number generator will be used to determine if the patient will have LB plus bupivacaine or bupivacaine for their interscalene block. The primary investigator will access the number generator in the pre-op area immediately prior to block placement. The website www.random.org will be used as the random number generator.

The research assistant in this study will be blinded to the method of analgesia for the patient. This person will not be responsible for any clinical testing and will record all data in the protected database daily. They will not have any access to the patients' clinical records or chart. **Any questions from the patient will be referred to the on-call resident or staff on call.**

Study Duration: We anticipate the study to take approximately 1 year from the date of enrollment of the first patient. Patients will be in the study for 14 days and then their chart monitored for up to 30 days post surgery. The data analysis should take one month after full enrollment of the study.

Individually Identifiable Health Information: This study involves the use of individually identifiable health information. Please see attached HIPAA authorization form.

Use of Radiation: N/A

Use of Center for Magnetic Resonance Research: N/A

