6.0 Data and Specimen Banking

Storage and Access: All study data will be stored on excel spreadsheets stored in Box. Only the PI and members of the research team will have access to the data.

Data: The data from this study will be collected both from Epic and directly from the patient. The data collected includes: demographic data, age, weight, ASA class, duration of surgery, length of stay in recovery room both phase 1 and 2, length of hospital stay, amount of opioids given intraoperatively and post-operatively, non-opioid pain medication, pain score (0-10) at 2, 6, 24, 48, and 72 hours, satisfaction with treatment, Quality of Recovery survey at 72 hours and 14 days, and any adverse events.

Release/Sharing: N/A

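### The pain question changes from maximum to current when the patient goes home, and the plan does not say which score forms the 72-hour pain outcome

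*Combined protocol and SAP*

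**What the plan says.** The instructions for pain scores are spread over several sections of the combined protocol and SAP.

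- **Section 5.0, Study Procedures, ward or hotel.** Each day a team member is to "ask the patient their maximum pain score, total opioids and non-opioid pain medication used, and length of stay".
- **Section 5.0, Study Procedures, home.** After discharge home the team member is to "ask the patient their current pain score, total opioid pills taken and non-opioid pain medication taken", at 24, 48 and 72 hours. Home patients also keep a daily pain diary, whose content is not described.
- **Section 5.0, Assessments.** This paragraph sets contacts for all patients, in person or by telephone, at the same three times, each with a window of 5 hours either side. Its only instruction on the pain rating is "Patients will be asked to rate their pain on scale of 0-10". No recall period is given.
- **Section 6.0, Data.** The item listed is "pain score (0-10) at 2, 6, 24, 48, and 72 hours", again without saying maximum or current.
- **Section 3.0.** The secondary outcome is less pain over 72 hours: "Assessed via total pain scores (Use of Visual Analog Scale". Neither the item nor the meaning of a total is defined. The Study Summary is no more specific.
- **Section 15.0.** No pain score is named. The statistician is to work from the protocol.

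Low pain is one condition for going home: "If patients have met criteria for discharge to home including pain <4/10". Section 3.0 also lists faster readiness for discharge as a hypothesised effect of the study treatment.

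**The concern.** Maximum pain and current pain are different quantities. A maximum over a period that includes the present moment cannot be lower than the current score, and it will usually be higher. Read literally, the Study Procedures text lets the patient's location decide which quantity is recorded.

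Location is determined after randomisation, depends partly on pain, and may differ by arm. If one arm goes home sooner, more of its scores come from the item that can only be equal or lower. That arm would then look better even with identical pain. Blinding the assessor does not help, because the wording of the question produces the difference.

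At stake is the first-listed secondary outcome in a trial whose stated purpose (section 1.0) is to show superior pain control. If only one of the two items was asked, the other cannot be reliably recovered later.

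**Working it through.** **Comparing the text.** The plan gives no numerical figure on this point to reproduce, so the first check is what each section specifies.

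| Place | Who and when | Item |
|---|---|---|
| 5.0 Study Procedures | ward or hotel, each day | maximum |
| 5.0 Study Procedures | home, 24, 48, 72 h | current |
| 5.0 Assessments | in person or telephone, 24, 48, 72 h | 0-10, recall period not stated |
| 6.0 Data | 2, 6, 24, 48, 72 h | 0-10, recall period not stated |
| 3.0 Endpoints | over 72 h | total of pain scores, item not stated |
| 15.0 Statistics | not stated | not stated |

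The Assessments paragraph and section 6.0 may mean one uniform item. They do not say so, and they do not override the location-specific wording.

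**Illustration of size.** Sections 6.0 and 15.0 supply the five assessment times and 35 patients per arm. All other inputs are assumptions:

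- maximum exceeds current by 2 points (range 1 to 3);
- the share of patients at home differs between arms by 15 percentage points (range 10 to 20) at each of 24, 48 and 72 h;
- the SD of a single score is 2.5, and the correlation between scores is 0.5;
- the outcome is the sum of the five scores, compared by a two-sided 5% t-test.

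*Step 1. Spurious arm difference* = (maximum minus current) × (difference in share at home) × (number of assessments affected).

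- 2 × 0.10 × 3 = 0.6 points
- 2 × 0.15 × 3 = 0.9 points
- 2 × 0.20 × 3 = 1.2 points

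*Step 2. SD of the five-score total* = 2.5 × √(5 + 5 × 4 × 0.5) = 2.5 × √15 = 9.68.

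*Step 3. False-positive rate* from the noncentral t distribution with 68 df. The noncentrality is the standardised difference × √(35/2).

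| Gap (points) | Difference in share at home | Times affected | Artefact (points) | Artefact / SD | False-positive rate |
|---|---|---|---|---|---|
| 1 | 10% | 3 | 0.30 | 0.031 | 5.2% |
| 2 | 15% | 1 | 0.30 | 0.031 | 5.2% |
| 1 | 15% | 3 | 0.45 | 0.046 | 5.4% |
| 2 | 10% | 3 | 0.60 | 0.062 | 5.8% |
| 2 | 15% | 3 | 0.90 | 0.093 | 6.7% |
| 2 | 20% | 3 | 1.20 | 0.124 | 8.0% |
| 3 | 15% | 3 | 1.35 | 0.139 | 8.9% |
| 3 | 20% | 3 | 1.80 | 0.186 | 12.0% |

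*Step 4. Sensitivity of the 0.9-point case.* A correlation of 0.3 gives 7.3% and one of 0.7 gives 6.3%. An SD of 2 gives 7.7% and one of 3 gives 6.2%.

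*Step 5. Simulation.* Mixing two items also adds variance, which the formula ignores. A simulation of 100,000 trials with a 2-point gap, and each patient in the same location at all three times, allowed for this. Shares at home of 55% v 45% gave 5.8%, 57.5% v 42.5% gave 6.4%, and 60% v 40% gave 7.7%. Equal shares (50% v 50%) gave 5.0%.

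**The case against.** The strongest reply is that the outcome already has a natural source. The Assessments paragraph sets one 0-10 rating for everyone at 24, 48 and 72 hours, in person or by telephone, and section 6.0 lists one matching data item. Timing supports this. The maximum score is asked daily with no hour attached, whereas the current score is tied to the same three hours. Section 6.0 lists neither a maximum score nor the diary. The ward and hotel maximum could therefore be extra follow-up only. The data sheet named in section 5.0 is not among the documents and may fix the wording.

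A second reply is that bias needs several conditions together: both items are pooled, maximum clearly exceeds current, and the arms differ in the share actually at home. Faster readiness for discharge does not establish the last of these. Hotel patients stay on the maximum item, and section 5.0 separates readiness from departure for patients who are ready "but are awaiting placement, the time of discharge for the purposes of the study will be the day they have met such criteria".

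Much of this stands. It makes mixing less likely and the bias conditional, and the size rests on assumed inputs. It does not remove the conflict. The uniform reading is an inference, since no section says current or maximum for the scheduled score. Staff who follow the Study Procedures text as written would ask different questions by location at the same hours. Even on the uniform reading, the recall period is missing.

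**Conclusion.** The concern holds. The plan gives two different pain questions according to location after randomisation and does not say which forms the 72-hour pain outcome. If both are used, scores are not comparable across locations, and any bias favours the arm that is home sooner.

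The size cannot be established from the documents. Under the assumptions above, the central case is an artefact of about 0.09 SD, with a false-positive rate of 6.7% instead of 5% (5.8% to 8.0% for location differences of 10 to 20 percentage points). Across the full assumed grid the rate runs from 5.2% to 12.0%. It stays at 5% if one uniform item is used or the arms do not differ in location.

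The likely effect is modest and confined to this secondary outcome; the primary opioid outcome is untouched. The plan should still be corrected, because mixed items make the pain result hard to interpret even without bias. Confidence is medium, because the uniform reading cannot be excluded.

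**What to change.** Reconcile sections 3.0, 5.0 and 6.0 so that every patient is asked the same pain item, with one stated recall period, at 24, 48 and 72 hours, whether in hospital, hotel or home. Name that item in section 3.0 as the score used for the 72-hour pain outcome, and refer to it in section 15.0. State that no other pain item, and not the home diary, enters that outcome.

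The cost is a reworded question and a revised data sheet at contacts already planned. No visits are added and the sample size does not change. The change has to precede data collection to be fully effective.

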15.0 Statistical Considerations

Data Analysis Plan: We plan to collect our data using excel, which will be maintained in box. When the study is completed and ready for statistical analysis the data will be shared with our staff statistician.

Power Analysis: Following the pilot study of 30 patients, it was determined that 40 additional patients (for a total of 70 patients, 35 per group) would need to be enrolled to reach 80% power.

Statistical Analysis: This study will be analyzed by our staff biostatistician. The data will be deidentified and shared with him in box. The statistician will be provided the protocol so they are able to analyze for primary and secondary objectives.

Data Integrity: All patients will be assigned a unique patient identifier. The data that will be sent to the statistician will be deidentified.

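### The cost paragraph aims to identify the most cost-effective arm from cost totals alone, with no effect measure linked to cost and no interval stated

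*Combined protocol and SAP*

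**What the plan says.** The cost paragraph in Section 5.0 (Procedures Involved) states that the total cost of analgesics "will be tabulated at the conclusion of the study to determine the most cost effective treatment option". The reason given is that this figure will be "added into the cost of hospitalization including the number of days each patient spent in the hospital". That is all the plan says about method.

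Cost does not appear among the secondary objectives in the Study Summary, which are "Pain scores within 72 hours, QOR at 72 hours and 14 days, Number of phone calls to surgeon, adverse events, time to discharge", nor among the endpoints in Section 3.0. Section 15.0 (Statistical Considerations) leaves the analysis to the statistician: "The statistician will be provided the protocol so they are able to analyze for primary and secondary objectives".

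On hospital stay, an earlier paragraph of Section 5.0 deals with patients who are ready to leave but awaiting placement. For them "the time of discharge for the purposes of the study will be the day they have met such criteria". The plan explains that the date on which such a patient really leaves depends on when a place is found. Section 6.0 lists a single stay variable among the data collected: "length of hospital stay, amount of opioids given intraoperatively and post-operatively".

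**The concern.** Cost-effectiveness compares what is spent with what is gained. The paragraph describes only the spending side, so its conclusion does not follow from its analysis. A cheaper arm with more opioid use, more pain or a lower QoR-15 could still be labelled the most cost-effective.

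A tabulation with no interval also gives the reader no way to tell a real cost difference from a chance one in a trial of about 70 patients. One of two observed mean costs will be lower, barring an exact tie.

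The label could matter in practice. Section 2.0 says the liposomal product is already the institution's standard for these patients, so a cost-effectiveness statement from a randomised trial could be used to keep or drop it.

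A smaller gap is that the paragraph does not say whether hospital days stop when discharge criteria are met or when the patient actually leaves.

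**Working it through.** The plan gives no figure to reproduce here: no unit cost, cost SD, threshold or alpha. The check therefore has two parts.

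**1. Does any effect enter the comparison?** The stated quantity per patient is

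total = analgesic cost + hospitalization cost (including days in hospital).

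Changing a patient's pain score or QoR-15 leaves this total unchanged, so neither can alter the ranking of the arms. Opioid use enters only through the price of the drug, which is not a measure of benefit. Sections 3.0 and 15.0 and the Study Summary do not fill the gap. The effects themselves are collected (opioid amounts, pain to 72 hours, and Quality of Recovery at 72 hours and 14 days, all in Section 6.0), but none is tied to cost.

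**2. How far can chance decide which mean is lower?**

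Inputs:
- n = 35 per group, from Section 15.0.
- d = true difference in mean cost divided by the SD of per-patient cost. This is assumed and shown over a range, because the documents give no cost data.
- Equal SD in both arms and approximately normal sample means, both assumed.

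Formulas:
- Standard error of the difference, in SD units: √(2/35) = 0.239.
- 95% half-width: 1.96 × 0.239 = 0.47 SD.
- Probability that the lower observed mean belongs to the truly dearer arm: Φ(−d/0.239).
- Probability that the 95% interval includes zero: Φ(1.96 − d/0.239) − Φ(−1.96 − d/0.239).

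| Assumed d | Lower mean is in the dearer arm | 95% interval includes zero |
|---|---|---|
| 0 | no dearer arm; each arm is lower half the time | 0.95 |
| 0.1 | 0.34 | 0.93 |
| 0.2 | 0.20 | 0.87 |
| 0.3 | 0.10 | 0.76 |
| 0.5 | 0.02 | 0.45 |

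For d = 0.2: 0.2/0.239 = 0.837, and Φ(−0.837) = 0.20. For modest true differences, the lower total is often in the wrong arm, and an interval would usually have warned the reader.

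**3. Hospital days.** Set side by side, the discharge paragraph defines discharge for study purposes as the day criteria are met when a patient awaits placement. The cost paragraph speaks of days spent in hospital without saying which end date is used, and Section 6.0 names one stay variable without defining it. Both readings are open. The effect on cost cannot be calculated, because the documents give no frequency or length of placement delay and no daily cost.

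**The case against.** The strongest reply is that this is one exploratory paragraph. Cost is not a primary or secondary objective and does not drive the sample size. The text calls the work an analysis, does not rule out an interval, and sets no rule that the lower point estimate wins. The coin-flip result under equal costs is true of any two-arm point comparison. These points stand as limits on severity, and they are why the text supports saying that the cheaper arm *can* be so named, not that it must be. They do not supply the missing effect measure.

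Two stronger readings are tempting, and the documents do not support them.

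- **A contradiction on hospital days.** A reader might infer that the cost count includes the placement days that the discharge rule removes. The text does not establish this. Both statements are in Section 5.0, and the discharge rule is set for study purposes, so it may govern the cost count too. Even if actual days are meant, a cost analysis may properly count bed-days that were used. What remains is an ambiguity.
- **Hotel nights and readmissions left out.** A reader might infer this because the cost paragraph names neither. But its wording on hospitalization cost is not an exhaustive list, readmission days are also days in hospital, and charts are followed to 30 days. Whether hotel nights belong depends on the costing perspective, which the plan does not state.

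**Conclusion.** The concern holds in a limited form. The stated analysis can rank the arms by cost but cannot show which is more cost-effective, because no effect is linked to cost and no interval is stated. At 35 per arm a difference in mean cost smaller than about 0.47 SD would lie within its own 95% margin. The chance that the lower mean points to the wrong arm runs from 0.34 at a true difference of 0.1 SD to 0.02 at 0.5 SD. The half-width and these probabilities rest on the stated group size, a normal approximation and equal SDs. The true differences are assumed.

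The definition of hospital days is unresolved rather than contradictory, and no size can be put on it from the documents. Severity is minor: the primary and listed secondary results are unaffected.

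**What to change.** 1. Rename the analysis a descriptive cost comparison. Report the difference in mean cost between randomised arms with a bootstrap 95% interval.
2. Use the term cost-effective only if the cost difference is shown jointly with the difference in an effect already collected, such as the 72-hour opioid total or QoR-15. Resample patients within arm and keep each patient's cost and effect together.
3. State whether hospital days follow the criteria-met rule or actual discharge, and give the other as a sensitivity analysis. Either may lead if chosen in advance.
4. State the costing perspective and the source of unit costs.

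The cost is a few sentences of plan text and modest programming. Unit costs must also be sourced, since Section 6.0 does not list them among the data collected. For patients awaiting placement, both the criteria-met day and the actual discharge day must be kept. The real downside is that the analysis may be unable to name a winner.
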